6 TREATMENT

6.1 Treatment Administered

Subjects who fulfill all the inclusion and none of the exclusion criteria may be accepted in the study. Each subject should read and sign an informed consent form prior to any screening procedures being performed. This study involves a comparison of an intralesional injection of CANDIN with an intralesional injection of placebo (unpreserved normal saline solution) in common warts. Subjects will receive one (Cohorts 1 and 2) or more (Cohort 3) intralesional injections every two weeks (14 +/- 2 days) at the region of the interdigitated base of wart (epidermal/dermal junction) for up to 20 weeks (a maximum of 10 doses per subject) or up to resolution of all injectable warts. Subjects who experience local tolerance issues when dosing is performed at 2-week intervals may be injected at 3-week intervals (21 +/- 2 days) also for a maximum of 10 doses per subject.

Subjects will be included in three cohorts as follows:

- 1. Cohort 1: Approximately 52 subjects will receive 0.3 mL of either CANDIN (n=39) or placebo (n=13) intralesionally in the largest common wart (primary) every second week (14 +/- 2 days) for a maximum of 10 injections. If the primary common wart exhibits a complete response, the second largest injectable common wart of all anatomical regions will be injected with CANDIN at the same dose. If the second largest common wart exhibits a complete response, the third largest of all anatomical regions will be injected. If an injected wart recurs after exhibiting a complete response, it will be re-injected instead of the non-primary injected wart that was injected at the previous visit. This injection strategy will be repeated for a maximum of 10 injections per subject or until all injectable common warts exhibit a complete response, if it occurs before all 10 injections are used.
- 2. **Cohort 2:** Approximately 52 subjects will receive 0.5 mL of either CANDIN (n=39) or placebo (n=13) intralesionally in the largest common wart every second week (14 +/- 2 days) for a maximum of 10 injections. If the primary common wart exhibits a complete

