Nielsen- CFW-2D Page 26 of 54 Protocol Final version 5.0: 06Dec2016 response the second largest injectable common wart of all anatomical regions will be injected with CANDIN at the same dose. If the second largest common wart exhibits a complete response the third largest wart of all anatomical regions will be injected. If an injected wart recurs after exhibiting a complete response, it will be re-injected instead of the non-primary injected wart that was injected at the previous visit. This injection strategy will be repeated for a maximum of 10 injections per subject or until all injectable common warts exhibit a complete response, if it occurs before all 10 injections are used.

3. Cohort 3: If the safety data of the 2nd cohort support continuation of the study (defined as medical assessment of the first eight (8) subjects (of cohort 2) completing three (3) injections), the approximately 52 subjects of cohort 3 will receive either 0.3 mL/wart CANDIN (n=39) or placebo (n=13) (total per visit ≤ 1.2 mL). Subjects in cohort 3 must have injectable common warts in at least 2 different anatomic regions. CANDIN or placebo will be injected under the largest wart (primary) per major anatomical region (left or right; arm, hand, leg, foot (excluding sole) or the torso) for a minimum of two (2) and a maximum of four (4) injections per visit every second week (14 +/- 2 days) for a maximum of 10 visits with injections. No more than one wart per anatomical region will be injected on any given visit. If any primary injected wart exhibits a complete response, the next largest injectable common wart will be injected with CANDIN at the same dose (maximum of 4 injections per visit) providing the new injectable wart is not within the same anatomical region as other currently injected warts. If an injected wart recurs after exhibiting a complete response, it will be re-injected instead of the non-primary injected wart that was injected at the previous visit. This injection strategy will be repeated for a maximum total of 10 injection visits per subject or until all injectable common warts exhibit a complete response, if it occurs before the end of the 10 injection visits.

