2.3 Exploratory Objectives

3 STUDY OVERVIEW

3.1 Study Design

This is a placebo-controlled, double-blind (subject, Investigator, and site staff with the exception of unblinded dedicated staff to handle study medication), multi-center, Phase IIa study with 3 dose cohorts, randomized to Candin or placebo in a 3:1 ratio. The main study will be up to 20 weeks (10 doses administered every other week) or until a subject has complete resolution of all injected common warts. Subjects who cannot tolerate dosing every 2 weeks (14 ± 2 days) due to a local tolerance issue may be injected at 3-week (21 ± 2 days) intervals for up to 10 doses, increasing the length of the study to 29 weeks. Subjects will be followed for 4 months after final injection(s) for evidence of new or reoccurring warts and for safety evaluation.

Approximately 156 (male or female) subjects aged 18 to 65 inclusive at the date of consent, with 3 to 20 common warts on hands, feet (excluding soles), limbs, and/or trunk will be included in this study. It is assumed that approximately 80% of the subjects will either complete the study or reach complete resolution. Drop-outs will not be replaced. Refer to Section 9 for sample size and power of the study.

Subjects will be included in three cohorts as follows:

Cohort 1: Approximately fifty-two subjects will receive 0.3 mL of either Candin (n=39) or placebo (n=13) intralesionally in the largest (primary) common wart every second week (14 ± 2 days) for a maximum of 10 injections. If the primary common wart exhibits a complete response, the second largest injectable common wart of all anatomical regions will be injected with the randomized study medication at the same dose. If the second largest common wart exhibits a complete response, the third largest wart of all anatomical regions will be injected. If an injected wart recurs after exhibiting a complete response, it will be re-injected instead of the non-primary injected wart that was injected at the previous visit. This injection strategy will be repeated for a maximum of 10 injections per subject, or until all injectable

common warts exhibits a complete response if that occurs before all 10 injections are used.

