Cohort 2: Approximately fifty-two subjects will receive 0.5 mL of either Candin (n=39) or placebo (n=13) intralesionally in the largest (primary) common wart every second week $(14 \pm 2 \text{ days})$ for a maximum of 10 injections. The same procedures will be followed in the event of complete response or recurrence as described for Cohort 1.

Cohort 3: If the safety data from Cohort 2 support continuation of the study (defined as medical assessment of the first eight subjects of Cohort 2 completing three injections), approximately 52 subjects planned for Cohort 3 will receive either 0.3 mL/wart Candin (n=39) or placebo (n=13), with a total per visit not to exceed 1.2 mL. Subjects in Cohort 3 must have injectable common warts in at least 2 different anatomic regions. Candin or placebo will be injected under the largest (primary) wart per major anatomical region (left or right; arm, hand, leg, foot excluding sole, or the torso) for a minimum of two and a maximum of four injections per visit, every second week (14 ± 2 days) for a maximum of 10 visits with injections. No more than one wart per anatomical region will be injected on any given visit. If any primary injected wart exhibits a complete response, the next largest injectable common wart will be injected with the randomized study medication at the same dose (maximum of 4 injections per visit), providing the new injectable wart is not within the same anatomical region as other currently injected warts. (If an injected wart recurs after exhibiting a complete response, it will be reinjected instead of the non-primary injected wart that was injected at the previous visit.) This injection strategy will be repeated for a maximum total of 10 injection visits per subject or until all injectable common warts exhibit a complete response, if it occurs before the end of the 10 injection visits.

Two Follow-up visits are included in the study to further assess the efficacy and safety of the study medication. Follow-up information will be obtained for subjects who discontinue their participation in the study. All procedures scheduled for during Follow-up Visit 1 and Follow-up Visit 2 should be completed for early termination subjects, as well as for those subjects who have complete resolution of all common warts prior to their Efficacy Evaluation visit (V13).

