3.3 Randomization Schedule and Blinding Procedures

This is a double-blind study defined as blinding of subjects, investigators, and site personnel not involved in study medication preparation and accountability. A concealed, centralized randomization list generated by an unblinded Sponsor representative will be used to assign the cohort and treatment to the subjects using an internet-based system. Randomization will be unbalanced (3:1) in favor of Candin. To maintain the blind, a qualified, unblinded person at each study site will prepare the syringes containing the medication (CANDIN or saline) independently from the Investigator performing the injection and making the evaluations. Subjects will be randomly assigned to cohorts first, and then to treatment, according to Table 2.

Randomization Number of Number of Number of Ratio between Randomized Randomized Subjects in **Anatomical Regions Subjects** to Candin to Placebo **Cohorts within Cohorts** Stratum Cohort 1 = 3325 8 Single 66 1:1 Cohort 2 = 3325 8 Cohort 1 = 1914 5 5 Multiple 90 4:4:11 Cohort 2 = 1914 Cohort 3 = 52

Table 2. Randomization Structure by Stratum, Cohort, and Treatment

The first 16 subjects will be randomized (1:1) to Cohort 1 or 2 until medical assessment of the first eight subjects of Cohort 2 (6 on active and 2 on placebo) completing three injections supports continuation of the study to Cohort 3. Once medical assessment supported continuation of the study to Cohort 3, subsequent subjects with warts in at least 2 different anatomical regions will be randomized to Cohort 1, 2, or 3 in a ratio of 4:4:11 to ensure that the treatment assignment for the overall 156 subjects will approximately preserve the above randomization structure.

The treatment randomization assignments will be kept secured from the Investigator and/or blinded site staff in the unblinded pharmacy binder until the database is finalized and hard locked.

The investigational site will assign each subject a subject identifier number during screening that will be used on all subject documentation throughout the study. Numbers will be assigned in ascending order using Sponsor's numbering system.

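### Protocol 6.1 says the next wart after a complete response is injected with CANDIN in both arms, while SAP 3.1 says randomized study medication: an inconsistent dosing instruction, almost certainly a drafting slip

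*Protocol*

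**What the plan says.** Protocol 6.1 describes the trial as a comparison of intralesional CANDIN with intralesional saline and assigns 39 subjects to CANDIN and 13 to placebo in each cohort. It then gives the rule for moving to another wart after a complete response:

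- Cohort 1: "the second largest injectable common wart of all anatomical regions will be injected with CANDIN at the same dose".
- Cohort 2: after a complete "response the second largest injectable common wart of all anatomical regions will be injected with CANDIN at the same dose".
- Cohort 3, when any primary wart clears: "the next largest injectable common wart will be injected with CANDIN at the same dose", "providing the new injectable wart is not within the same anatomical region as other currently injected warts".

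The sentences in 6.1 on the third wart (Cohorts 1 and 2) and on re-injecting a recurred wart (all cohorts) name no product.

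SAP 3.1 restates the procedure. For Cohort 1 the next wart "will be injected with the randomized study medication at the same dose". For Cohort 2, "The same procedures will be followed in the event of complete response or recurrence as described for Cohort 1". For Cohort 3, "the next largest injectable common wart will be injected with the randomized study medication at the same dose".

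On supply, SAP 3.3 says that an unblinded person at each site "will prepare the syringes containing the medication (CANDIN or saline) independently from the Investigator performing the injection".

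**The concern.** This is a dosing rule, and it sits in the document that instructs sites. The SAP has the right wording but does not tell anyone what to draw up. The Investigator who injects is blinded and could not notice a wrong product; only the unblinded preparer could act on the sentence. In the Cohort 3 paragraph the sentence on primary warts names both products and the next-wart sentence names only CANDIN, so a literal-minded reader could take the change as deliberate.

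If it were followed as written, some control subjects would become partly treated subjects. Their later wart outcomes and later treatment-emergent adverse events (TEAEs) would no longer describe placebo. SAP 5.3 analyses safety by the dose received, but the available text gives no rule for a subject who received both products. In Cohort 3 the primary comparison could also be touched.

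**Working it through.** The plan states no figure on this point, so there is nothing to reproduce. The check is a comparison of texts, followed by arithmetic to see whether the consequence can be sized.

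**Step 1. Product named for the next wart**

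| Cohort | Protocol 6.1 | SAP 3.1 |
|---|---|---|
| 1 | CANDIN | randomized study medication |
| 2 | CANDIN | as Cohort 1, by cross-reference |
| 3 | CANDIN | randomized study medication |

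The two documents disagree in all three cohorts.

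**Step 2. What could reach the primary endpoint**

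The endpoint (Protocol 3.1, SAP 4.1) is complete resolution of the primary injected wart(s) at any treatment or follow-up visit.

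- Cohorts 1 and 2 have one primary wart. The next-wart rule starts only after that wart has resolved, so the endpoint is already met, and a later recurrence does not undo it. Affected on the primary endpoint: 0 of 13 + 13 = 26 placebo subjects.
- Cohort 3 has two to four primary warts, and the rule starts when any one of them resolves. Reading the endpoint as requiring all of them, a placebo subject could receive CANDIN before the endpoint is decided. This concerns only the 13 placebo subjects of Cohort 3, out of 3 × 13 = 39 in the pooled placebo group. The CANDIN would go into a new wart, so it changes the endpoint only if it helps a primary wart elsewhere. Any such help would raise the placebo rate and so bias toward no difference.

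**Step 3. How many placebo subjects might trigger the rule**

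Inputs: a 24% placebo complete-resolution rate (Protocol synopsis, Sample Size Determination), and roughly 30% of subjects with spontaneous regression of at least one wart in nine months (Protocol 1.1). Applying either to this event is an assumption.

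*Cohorts 1 and 2*
- All resolutions occur in time: 0.24 × 26 = 6.2.
- Only resolutions by the last injection visit count (V12, week 18, of 36 weeks to V15 on the two-week schedule), with a constant hazard: 1 − 0.76^(18/36) = 12.8%, and 0.128 × 26 = 3.3.

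*Cohort 3 (any one primary wart resolves)*
- 30% any-wart figure: 0.30 × 13 = 3.9.
- Warts clear independently at 24% each, two warts: 13 × (1 − 0.76²) = 5.5.
- The same with four warts: 13 × (1 − 0.76⁴) = 8.7.

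*Sum with the 6.2 above*
- 6.2 + 3.9 = 10.1 of 39 (26%).
- 6.2 + 5.5 = 11.7 of 39 (30%).
- 6.2 + 8.7 = 14.9 of 39 (38%).

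None of these is a bound. The 30% is a natural-history figure, not a rate for saline-injected warts. The 24% is a rate per subject, not per wart. Warts on one subject may clear together. A switch in Cohort 3 also needs another eligible wart in a region not currently being injected.

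**The case against.** The strongest reply is that nobody would follow the sentence literally. The study is double-blind, treatment is assigned by subject, and syringes hold either CANDIN or saline. Read literally, Cohort 3 would have a placebo subject receive saline in one wart and CANDIN in another at the same visit, and nothing in the endpoints, populations or visible analyses describes such a crossover. Protocol 14.5.2 also refers to the first injection at Visit 3 as one with CANDIN when defining TEAEs for all subjects, so the loose use is a habit of the text. The SAP, dated February 2018, postdates Protocol version 5.0 of December 2016 and has the right wording. Protocol 6.2.1 already requires dispensing records and sponsor verification of accountability, and SAP 6.4 settles important deviations before unblinding and database lock.

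All of this stands, and it keeps the severity low. It does not remove the inconsistency: no visible Protocol text corrects the instruction. Most visit procedures in Protocol section 7 and parts of 6.2 are not in the public text, so a clarification there cannot be excluded.

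Three stronger readings are tempting and are not supported:

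- *Placebo subjects were meant to cross over, or did receive CANDIN.* The design text points the other way, and nothing shows that it happened.
- *The primary comparison is compromised throughout.* Step 2 confines any exposure to Cohort 3.
- *The count in Step 3 is an estimate or a ceiling.* It moves with assumptions that the documents do not settle.

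**Conclusion.** The three sentences of Protocol 6.1 are wrong as written and conflict with SAP 3.1. This is an internal inconsistency, almost certainly a drafting slip and not a design choice, and its severity is low.

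If the rule were followed literally, the primary endpoint would be unaffected in Cohorts 1 and 2; only outcomes of later warts and attribution of later TEAEs would suffer. In Cohort 3 the primary endpoint could be affected, in the direction of no difference. Neither the number of subjects nor the size of the bias can be estimated from the documents. The Cohort 3 figures of about 4 of 13, and 5.5 to 8.7 of 13, only illustrate how far the answer depends on the per-wart assumption. The finding itself rests on the wording and not on these figures.

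**What to change.** In the three sentences of Protocol 6.1, replace *with CANDIN* by *with the randomized study medication*, as SAP 3.1 already has it.

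Use the drug-accountability verification already required by Protocol 6.2.1 to have unblinded staff confirm, before database lock, that no placebo subject received CANDIN intralesionally. The DTH skin test uses the same product in every subject, so the check must separate that use.

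Only if a case is found: add a sensitivity analysis of the primary endpoint using data up to the first CANDIN injection, and report that subject's later TEAEs separately.

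The cost is three phrases and one added question in a check that is already planned. The analysis does not change unless a case is found.

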6.2 Materials and Supplies

6.2.1 Study Products

DTH Testing: CANDIN (Candida albicans Skin Test Antigen for Cellular Hypersensitivity) used according to the US approved labeling. CANDIN is a clear, colorless, sterile aqueous solution, pH of 8.0-8.5, packaged in 1 mL multidose glass vials. Each vial delivers 10 x 0.1 mL dose. CANDIN will be provided by Nielsen BioSciences, Inc.

Investigational Product: CANDIN used as the Investigational Product (IP). CANDIN is a clear, colorless, sterile aqueous solution, pH of 8.0-8.5, packaged in 1 mL multidose glass vials. Each vial delivers 10 x 0.1 mL dose. CANDIN will be provided by Nielsen BioSciences, Inc.

Placebo: 0.9% sodium chloride injection, USP, preservative free for injection used as the placebo. It will be provided by Nielsen BioSciences, Inc. Each vial will be used for a single injection (once) since the contents are not preserved.

The Investigator will be responsible for drug accountability. After verification of the drug accountability by the Sponsor, the Investigator will return the remaining study product (used and unused vials) to the Sponsor.

CANDIN for DTH testing and for use as the IP will be provided by the Sponsor to the Investigator and will be kept on site in a secure temperature controlled refrigerated space (2-8 °C). It will only be dispensed to

Nielsen- CFW-2D Page 27 of 54

subjects enrolled on the trial under the supervision of the Investigator. Refrigerator temperature will be monitored and recorded in a log. The Investigator is responsible for maintaining accurate records of the dispensing of study medication.
6.2.2 Method of Assignment to Treatment
This is a double-blind study defined as blinding of subjects, investigators, and site personnel not involved in study drug preparation and accountability.
Randomization will be unbalanced (3:1) in favor of CANDIN.
The subjects will be randomly assigned to cohorts first and then to treatment according to the following randomization table. The purpose is to ensure that subject characteristics are as comparable as possible between different cohorts.

used on all subject documentation throughout the study. Numbers will be assigned in ascending order using Sponsor's numbering system. 6.2.4 Breaking of Study Blinding This will be a double-blind study; the Investigators performing the injection, site personnel performing or recording study assessments, site study coordinators, and subjects will remain blinded to active versus control treatment.

The investigational site will assign each subject a subject identifier number during screening that will be

[figure not shown]

6.2.6 Assessment of Compliance

Since all study drug will be administered on site, compliance will be directly monitored by the study staff.

[figure not shown]
7 STUDY PROCEDURES

7.1 Screening Visits 1 and 2 (Day -30 to Baseline)

7.8 Vital Signs

The following vital signs will be recorded at Screening (V1), Baseline (V3) and Injection (V4-V12) Visits prior to treatment and Efficacy Evaluation Visit (V13) after an approximately 5 minutes resting period in a seated position:

- Systolic and diastolic blood pressure (mm Hg),
- Pulse (bpm),
- Body temperature (°C)

The weight (kg or lbs) and height (cm or inches) will be recorded at the Screening Visit (V1) only.

7.10 Physical Examination

A physical examination will be performed at Screening (V1) and Efficacy Evaluation Visit (V13). The following sites/systems will be included in the physical examination. Each system will be scored as normal/abnormal. Pertinent details must be recorded for any clinically significant findings, in order to be added as medical history or an AE.

- General appearance
- Skin
- Eyes, Ears, Nose, Throat
- Head, Neck, Thyroid
- Lymphatic
- Cardiovascular
- Lungs, Chest
- Abdomen
- Extremities
- Musculoskeletal
- Neurologic

7.12 DTH Challenge

At Screening Visit 1 (V1), the DTH test will be done by administering a single intradermal injection of CANDIN (0.1mL) on the volar surface of the forearm or on the outer aspect of the upper arm, at least 2 cm away from any primary injectable wart(s). The skin should be cleansed with 70% alcohol before applying the skin test. The intradermal injection must be given as superficially as possible causing a distinct, sharply defined bleb. An unreliable reaction may result if the product is injected subcutaneously. The subject will

Nielsen- CFW-2D Page 35 of 54

be asked to remain in the clinic for 30 minutes after receiving the injection of CANDIN for the DTH test, to assess any immediate reactions. A DTH diary will be handed to the subject, in order to capture any delayed reactions, prior to Screening Visit 2 (V2).

The test should be read on V2 at $(48 \pm 4 \text{ hours post DTH challenge injection that occurred at V1})$ by visually inspecting the test site and palpating the indurated area. Measurements should be made across two diameters. The mean of the longest and midpoint orthogonal diameters of the indurated area should be reported as the DTH response.

The measured DTH response must be between ≥ 5 mm and ≤ 25 mm in diameter to be considered a valid reaction. Responses <5 mm or >25 mm would exclude the subject from the study.

